**Table 22: Cairo-Bishop clinical TLS definition and grading**

| Complication       | Grade                 |                            |   |  |  |       |
|--------------------|-----------------------|----------------------------|---|--|--|-------|
|                    | 0                     | 1                          | 2   | 3  | 4  | 5     |
| Creatinine         | $\leq 1.5 \times$ ULN | 1.5 x ULN                  | $>1.5\text{-}3.0 \times$ ULN  | $> 3.0\text{-}6.0 \times$ ULN  | $> 6.0 \times$ ULN   | Death |
| Cardiac arrhythmia | None                  | Intervention not indicated | Nonurgent medical intervention indicated  | Symptomatic and incompletely controlled medically or controlled with device (e.g., defibrillator)  | Life-threatening (e.g., arrhythmia associated with HF, hypotension, syncope, shock)  | Death |
| Seizure            | None                  | -                          | One brief, generalized seizure; seizure(s) well controlled by anticonvulsants or infrequent focal motor seizures not interfering with ADL | Seizure in which consciousness is altered; poorly controlled seizure disorder; with breakthrough generalized seizures despite medical intervention | Seizure of any kind which are prolonged, repetitive or difficult to control (e.g., status epilepticus, intractable epilepsy) | Death |

## APPENDIX F: MAGROLIMAB PK AND ADA SAMPLE COLLECTION, PROCESSING, AND SHIPPING INSTRUCTION

### Sample Collection, Processing, and Shipping Instructions (PK/ADA)

#### A Phase 1 Study of Venetoclax with Obinutuzumab and Magrolimab (VENOM) in Relapsed and Refractory Indolent B-cell Malignancies

[figure not shown]
##### **Red Top Serum Separator Tube SST (PK, ADA)**

1. Fill a Red top SST COMPLETELY, as far as the vacuum will allow.
2. Mix immediately by gently inverting the tube 5 times.
3. Allow blood to clot undisturbed for 30 minutes (max. 60 minutes), tube standing upright.
4. Centrifuge tube within 1 hour of collection for 10-15 minutes at 1800 g until clot and serum are separated by a well -formed polymer barrier. *If serum and cells have not completely separated, re-centrifuge the specimen for an additional 6-8 minutes.*
5. Transfer serum, using a transfer pipette, into the Transport Tube (s).
6. Allow enough space between serum and tube caps to account for expansion during freezing. Do not overfill.
7. Record the subject ID number on the specimen label.
8. Wrap a small piece of parafilm around the cap of the transport tube. See parafilm instructions below.
9. Store serum samples for a minimum of 8 hours at **-80°C** until shipment to **PPD Richmond**.

| Visit                         | Collection Tube   | Tube Label  | Shipping Temp |
|-------------------------------|-------------------|---|---------------|
| C1D1, C3D1, C5D1, C9D1, C13D1 | 1 x 3.5mL Red SST | Collection Tube:
PK SST
Transport Tube:
PK 1
PK 2    | Frozen        |
| C1D1, C3D1, C5D1, C9D1, C13D1 | 1 x 3.5mL Red SST | Collection Tube:
ADA SST
Transport Tube:
ADA 1
ADA 2 | Frozen        |

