### 3.2.1 Magrolimab Administration

All patients will receive a magrolimab priming dose of 1 mg/kg on Day 2 of the first cycle of treatment. The duration of infusion of the priming dose will be 3 hours ( $\pm 30$  minutes). Use of an inline filter is required. All subsequent loading or maintenance doses of magrolimab will be infused over a duration of 2 hours ( $\pm 10$  minutes). When both obinutuzumab and magrolimab are given on the same visit day, obinutuzumab will be administered at least 1 hour after the completion of

magrolimab administration. All patients should be monitored for 1 hour post-infusion for all doses during Cycle -2. Post-infusion monitoring should begin after the last study drug is given. Post-infusion monitoring is not required for doses after Cycle 1, Day 22 for Arms 1 and 2 (dose-finding arms), and Cycle -2, Day 22 for Arms 3 and 4 (dose expansion arms). Patients who experience any treatment-related AEs during the observation period should be further monitored, as clinically appropriate.

Complete Blood Count with Differential will be performed prior to each dose, and 3-6 hours after the first and second doses of magrolimab - Cycle 1, Days 2 and 8 for dose-finding arms (Arms 1 and 2), and Cycle -2, Days 2 and 8 for dose-escalation arms (Arms 3 and 4). Complete Blood Count with Differential will also be performed twice weekly for the first cycle (Cycle 1 for dose-finding arms [Arms 1 and 2], and Cycle -2 for dose-escalation arms [Arms 3 and 4]).

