**Research Samples Calendar – Bloods:**

| Sample   | Collection Details*               | Baseline | Time Points # |             |              |               |               |  |  |                          |                                    |    | Supervising Laboratory/ Investigator |  |
|--|-----------------------------------|----------|--------------------------|-------------|--------------|---------------|---------------|--|--|--------------------------|------------------------------------|----|--------------------------------------|--|
|  |                                   |          | Window †      |             |              |               |               | Triplet Combination Therapy            |  |                          | Post-Treatment                     | PD |                                      |  |
|  |                                   |          | Cycle -2 D1              | Cycle -2 D8 | Cycle -2 D15 | Post-Cycle -2 | Post-Cycle -1 | D1 of Cycles 1, 3, 7 & 11 Δ | D1 of Cycles 1, 3, 5 & 9; Post-Cycle 12 δ | Post-Cycles 3, 6, 9 & 12 | Years 1-2= q3mos; Years 2-5= q6mos |    |                                      |  |
| cfDNA/ctDNA, Mutational panels (liquid biopsy), Plasma banking | 1 x 10 mL Streck tubes            | X        |                          | X           | X            | X             | X             |  |  | X                        | X                                  | X  | [name]                                 |  |
| Immune subsets, Protein, Immune Markers                        | 2 x 8-10 mL CPTs (sodium citrate) | X        |                          | X           | X            | X             | X             |  |  | X                        | X                                  | X  |                                      |  |
| Cytokine analysis, Serum banking                               | 1 x 10 mL in SST tube             | X        |                          | X           | X            | X             | X             |  |  | X                        | X                                  | X  |                                      |  |
| Flow cytometry   | Peripheral blood per SOC          | X        |                          | X           | X            | X             | X             |  |  | X                        | X                                  | X  | NCI LP                               |  |

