| Magrolimab pharmacokinetics                                    | 1 x 3.5mL in red SST              |          | X                        |             |              |               |               | X                                      | X  |                          |                                    |    | [name]/ PPD Richmond                   |  |
| Magrolimab ADA   | 1 x 3.5mL in red SST              |          | X                        |             |              |               |               | X                                      | X  |                          |                                    |    | [name]/ PPD Richmond                   |  |

\* Tubes/media may be adjusted at the time of collection based upon materials available or to ensure the best samples are collected for planned analyses.

# All timeframes may be adjusted to similar windows as the Study Calendar ([Appendix G](#)).

† Samples from the window period will be available only for patients enrolled in dose-expansion cohorts (Cohorts 3, 4, 5 and 6).

Δ For patients in dose-expansion cohorts (Cohorts 3, 4, 5 and 6).

δ For patients in dose-finding cohorts (Cohorts 1 and 2).

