### **10.4.9 Exploratory Analyses**

The following are the exploratory analyses planned:

- Overall response rate (ORR) after doublet-combination therapy with magrolimab and obinutuzumab

- Complete molecular remission rate (CMR) by ctDNA assay or similar assays as they become available after doublet-combination therapy with magrolimab and obinutuzumab
- Complete molecular remission rate (CMR) by ctDNA assay or similar assays as they become available after triplet-combination therapy with magrolimab, obinutuzumab and venetoclax
- Lead time for ctDNA assay in detecting molecular relapse prior to clinical progression
- Identify potential biomarkers and molecular correlates that are associated with response and/or resistance to the study treatment
- Test immunogenicity of magrolimab and asses the effect of anti-drug antibodies (ADA) on the pharmacokinetics, pharmacodynamic markers, efficacy, and safety of magrolimab.

The ORR and CMR rates will be determined and reported from individual cohorts and histological diagnosis. Responses will also be reported with waterfall plots, when appropriate. The exploratory objectives such as seeking to identify potential biomarkers and molecular correlates that are associated with response and/or resistance to the study treatment, will be assessed using descriptive statistics as well as non-parametric methods such as exact Wilcoxon rank sum tests. The analyses will be done without formal adjustment for multiple comparisons, but in the context of the number of tests performed.

Magrolimab PK data will be summarized using summary statistics (mean, median, range, standard deviation, etc.) at each time point. The overall rate of ADA occurrence and type of ADA (e.g., transient vs persistent) will be summarized for all patients. PK in ADA positive and negative patients will be tabulated at each timepoint. If relevant, the impact of ADA occurrence on efficacy and safety will be assessed through summary statistics.

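### Appendix F gives one magrolimab PK/ADA visit list which, read by the protocol's cycle labels, contradicts Section 5.1 for the expansion cohorts and leaves out their pre-magrolimab sample

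*Combined protocol and SAP*

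**What the plan says.** Section 5.1 (research samples calendar for blood) has separate triplet-phase columns for the two phases. One reads "D1 of Cycles 1, 3, 7 & 11" and is footnoted to expansion Cohorts 3 to 6. The other reads "D1 of Cycles 1, 3, 5 & 9; Post-Cycle 12" and is footnoted to dose-finding Cohorts 1 and 2. The PK and ADA rows are also marked at Cycle -2 Day 1, and a footnote limits window samples to the expansion cohorts. Neither row has a mark in the Baseline column, so Cycle -2 Day 1 is the only pre-magrolimab PK/ADA sample scheduled in expansion.

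Appendix F ties visits to tubes and tube labels. It lists "C1D1, C3D1, C5D1, C9D1, C13D1" once for PK and once for ADA, identically, with no reference to cohort. Sections 5.2.2.4 and 5.3.8 send the reader to Appendix F for further detail. The Study Calendar (Appendix G) sends the reader to Section 5.1.

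On dosing, Section 3.2.1 states: "All patients will receive a magrolimab priming dose of 1 mg/kg on Day 2 of the first cycle of treatment". Under Table 12 that first cycle is Cycle -2 for expansion patients.

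On analysis, Section 10.4.9 states: "Magrolimab PK data will be summarized using summary statistics (mean, median, range, standard deviation, etc.) at each time point". It also tabulates PK by ADA status at each time point and summarises the overall ADA rate and type for all patients. Section 10.2 allows dose-finding patients treated at the expansion dose level to be analysed together with the expansion cohorts.

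**The concern.** Appendix F is the page a sample coordinator would have open when labelling and shipping tubes. For an expansion patient, its first visit (C1D1) comes after the two-cycle window, when magrolimab has already been given. Followed literally, the pre-magrolimab sample is not drawn.

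One exploratory objective in Section 1.1.3 is to test the immunogenicity of magrolimab and the effect of ADA on PK, efficacy and safety. Without a pre-exposure sample, a positive on-treatment ADA result cannot be classed as treatment-induced or pre-existing. The missed visit cannot be repeated later.

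A second, separate issue survives even if Section 5.1 is followed exactly. The same visit label stands for different prior exposure in the two phases, and the analysis section does not say whether a time point is a label or a time since first dose.

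**Working it through.** **Inputs.** Expansion sizes are 18 FL, 6 MZL, 12 MCL and 6 CLL, with up to 24 patients in dose-finding (Section 10.2). Magrolimab days are D2, 8, 15 and 22 in the first treatment cycle and D1 and 15 in every later one (Tables 11 and 12). Cycles last 28 days, except that Cycle 1 lasts 35 days in Arms 2 and 4.

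**Plan's own figures.** 18 + 6 + 12 + 6 = 42, and 24 + 42 = 66. Both match Section 10.2.

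**Scheduled doses before each sample.** Let k be the order of the cycle counted from first treatment. Doses before Day 1 of cycle k are 0 for k = 1 and 4 + 2(k − 2) for k ≥ 2. In dose-finding, k equals the protocol cycle number. In expansion, Cycle -2 is k = 1, Cycle -1 is k = 2, and protocol Cycle c is k = c + 2. Post-Cycle 12 in dose-finding is taken as k = 13.

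| Source and cohorts | Visits (Day 1) | k | Prior scheduled doses |
|---|---|---|---|
| Section 5.1, Cohorts 1–2 | C1, C3, C5, C9, post-C12 | 1, 3, 5, 9, 13 | 0, 6, 10, 18, 26 |
| Section 5.1, Cohorts 3–6 | C-2, C1, C3, C7, C11 | 1, 3, 5, 9, 13 | 0, 6, 10, 18, 26 |
| Appendix F by protocol label, Cohorts 3–6 | C1, C3, C5, C9, C13 | 3, 5, 7, 11, 15 | 6, 10, 14, 22, 30 |

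The two Section 5.1 schedules match exactly by prior doses. Appendix F, read by label, breaks that match.

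**Visit overlap in expansion.** Appendix F keeps 2 of the 5 Section 5.1 visits (C1D1, C3D1), omits 3 (C-2D1, C7D1, C11D1) and adds 3 (C5D1, C9D1, C13D1). The earliest sample follows 4 + 2 = 6 doses, so 0 of up to 42 expansion patients would have a pre-magrolimab sample.

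**Same label, different exposure.** This holds under Section 5.1 as well.

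- C1D1: 0 prior doses in dose-finding against 6 in expansion, that is day 0 against day 2 × 28 = 56 after first treatment.
- C3D1: 6 prior doses against 10. In FL this is day 56 (Arm 1) against 4 × 28 = 112 (Arm 3). In MZL, MCL and CLL it is 35 + 28 = 63 (Arm 2) against 28 + 28 + 35 + 28 = 119 (Arm 4).

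**The case against.** The strongest reply is that the baseline sample is already in the plan. Section 5.1 schedules it, the Study Calendar points to Section 5.1, and Appendix F is cited only for additional detail. The study runs at one institution, so there are no other sites to diverge. This stands, and it makes the loss conditional. A reader might infer that the expansion cohorts have no planned pre-dose sample; the documents do not support that.

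Next, the Appendix F numbers 1, 3, 5, 9 and 13 are exactly the ordinal treatment cycles on which both Section 5.1 schedules fall. Protocol numbering stops at Cycle 12, so C13D1 is not a protocol treatment visit. Read as ordinals, Appendix F agrees with Section 5.1 for every cohort, and this may explain the list. But the convention is stated nowhere, and elsewhere the protocol calls the first expansion cycle Cycle -2. Staff would reasonably read C1D1 as Cycle 1 Day 1.

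A reader might also infer that Section 10.4.9 plans to pool PK across phases by visit label. It does not say so. The reference to all patients belongs to the sentence on ADA rate and type, and Section 10.2 only permits joint analysis at the same dose level. Mixing is a risk left open, not a stated analysis. Nor should the on-treatment values be called troughs, since neither Section 5.1 nor Appendix F gives the draw time relative to the dose on those days.

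Finally, it would be too strong to say that the ADA objective fails without the baseline. On-treatment ADA and PK by ADA status could still be described. Section 5.1 also banks serum at baseline, which might allow rescue testing, although the plan does not provide for that use.

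**Conclusion.** The point holds in a limited form. Under the protocol's cycle labels, the Appendix F list is wrong for Cohorts 3 to 6; under an unstated ordinal convention it is right. Either way it needs correcting or explaining.

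If staff work from Appendix F, up to 42 of 66 planned patients would lack a pre-magrolimab PK/ADA sample, and treatment-induced ADA could not be separated from pre-existing reactivity in them. The 42 is a ceiling that assumes full expansion accrual and consistent use of Appendix F. The count of 6 prior doses assumes a completed window on schedule. Patients moved early to the triplet for progression would have had fewer, though at least the priming dose if it was given on Cycle -2 Day 2.

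The undefined time point in Section 10.4.9 is a separate ambiguity. It could place pre-dose values and values after 6 doses under one label.

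The objective is exploratory and summarised descriptively. The primary safety endpoint, the secondary endpoints, the dose-finding rules and the sample size are unaffected. The correction should still be made, because it is cheap and a missed pre-dose visit cannot be repeated.

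**What to change.** In Appendix F, split the visit table by cohort to match Section 5.1, for both PK and ADA:

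- Cohorts 1–2: C1D1, C3D1, C5D1, C9D1, post-Cycle 12.
- Cohorts 3–6: C-2D1, C1D1, C3D1, C7D1, C11D1.

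In Section 10.4.9, add one sentence stating that PK and ADA time points are indexed by treatment cycle or time since first magrolimab dose, not by protocol cycle label.

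The cost is one appendix table and one sentence. No samples are needed beyond those Section 5.1 already schedules, and treatment does not change.

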##### **Parafilm Instructions For Transport Tubes**

1. Obtain a small piece of provided parafilm.
2. Hold tight against the cap of the transport tube and the side of the tube. Be sure to use half the parafilm to cover the cap and half of the parafilm to cover the top part of the tube.
3. While holding the end of the parafilm in place, gently pull and stretch the parafilm. Be careful not to pull too tight or it will break.
4. Wrap the stretched parafilm around the outside of the cap and top of the tube.

**SHIPMENT PREPARATIONS**

| SPECIMEN | SHIPPING FREQUENCY   | COURIER/ DESTINATION | SHIPPING TEMPERATURE |
|----------|--|----------------------|----------------------|
| PK       | Primary – Weekly
Backup – With next shipment of primary samples | PPD Richmond         | Frozen               |
| ADA      | Primary – Weekly
Backup – With next shipment of primary samples | PPD Richmond         | Frozen               |

**SPECIMEN SHIPPING INSTRUCTIONS**

**Electronic Packing List (EPL) Instructions (PK, ADA):**

For each specimen collected, please record the subject ID, visit, and collection date. Please send a copy of the EPL in the below tabular format to [[contact]](mailto:[contact]), [[contact]](mailto:[contact]), and [[contact]](mailto:[contact]).

| Sponsor           | Protocol | Subject ID | Visit | Collection Date | Collection Time | Sample type (e.g. PK, ADA) |
|-------------------|----------|------------|-------|-----------------|-----------------|----------------------------|
| Forty Seven, Inc. | VENOM    | XXXX       | C1D1  | 01/01/1990      | HH:MM AM        | PK                         |

[figure not shown]

**Packaging Specimens into the Frozen Shipper (PK, ADA)**

When packing a frozen shipper please follow the below instructions. Ensure that there is sufficient layering of dry ice both under and on top of the frozen specimens, such that the specimens are 'sandwiched' between dry ice.

1. Place specimens in absorbent wrap(s). Ensure that the screw cap lids on the polypropylene tubes are firmly in place and threaded properly. Dry ice may cause the lids to loosen while in transit.
2. Place the absorbent wrap(s) into a specimen transport bag, and seal bag closed.
3. Using insulated gloves, place a layer of dry ice in the bottom of the foam cooler, completely covering the bottom of the cooler.
4. Fold and place the transport bag containing frozen samples on top of the layer of dry ice.
5. Fill the remaining portion of the cooler with dry ice, completely covering the transport bag and bottom layer of dry ice.

*Note: The amount of dry ice is critical to maintain constant temperature within the shipper during transport.*

6. Replace the foam lid on the insulated container.
7. Secure the flaps of the shipper and tape the box closed.
8. Please include a copy of the electronic packing list within the shipment.
9. Ship at your courier's earliest convenience.

## APPENDIX G: STUDY CALENDAR

| Procedure                                     | Screening              | Baseline         | Window Portion † |            | Triplet Combination Therapy Δ | Response-Based Therapy | Disease Evaluations                     |              | End of Treatment or PD            | Active Monitoring/ Surveillance Follow-Up |                                  |                             |
|---|------------------------|------------------|-----------------------------|------------|--|------------------------|---|--------------|-----------------------------------|---|----------------------------------|-----------------------------|
|   |                        |                  | C -2
D1                  | C -1
D1 | C1-C6
D1                              | C7-C12
D1           | Window C-1/
Pre-C1,
Cycles 6 & 12 | Cycles 3 & 9 |                                   | Safety (Day 30)                           | Follow-Up (Prior to PD)          | Survival (Post-PD)          |
| Scheduling Window (Days):                     | -28 to -1  | -28  | -14* or -7 Δ     | -3         | -3                                       | -3                     | Last 7 days of the cycle                |              | Treatment discon./PD  | +7  | Every 3 or 6 months  | Every 3 months  |
| Confirmation of Diagnosis                     | X                      |                  |                             |            |  |                        |   |              |                                   |   |                                  |                             |
| Physical Exam                     | X                      | X                | X                           | X          | X  | X                      |   |              | X                                 | X   | X                                |                             |
| ECOG PS                                       | X                      | X                | X                           | X          | X  | X                      |   |              | X                                 | X   | X                                |                             |
| CBC with Differential             | X                      | X                | X*                          | X          | X  | X                      |   |              | X                                 | X   | X                                |                             |
| Chemistry Panels                  | X                      | X                | X*                          | X          | X  | X                      |   |              | X                                 | X   | X                                |                             |
| LDH   | X                      | X                | X*                          | X          | X  | X                      |   |              | X                                 | X   | X                                |                             |
| Total protein                                 |                        | X                | X*                          | X          | X  | X                      |   |              | X                                 | X   | X                                |                             |
| PT/INR and aPTT                               | X                      | X                | X                           | X          | X  | X                      |   |              | X                                 | X   | X                                |                             |
| Urinalysis                                    | X                      | X                | X*                          | X          | X  | X                      |   |              | X                                 | X   | X                                |                             |
| Pregnancy Test (urine/serum; WOCBP)           | X                      | X                | X Δ              | X          | X  | X                      |   |              | X                                 | X   |                                  |                             |
| Hepatitis and HIV Testing                     | X                      |                  |                             |            |  |                        |   |              |                                   |   |                                  |                             |
| Haptoglobin                                   |                        | X                |                             |            |  |                        |   |              |                                   |   |                                  |                             |
| Quantitative serum immunoglobulin (IG) levels |                        | X                | X                           | X          | X  | X                      |   |              | X                                 | X   | X                                |                             |
| Beta-2 microglobulin                          |                        | X                | X                           | X          | X  | X                      |   |              | X                                 | X   | X                                |                             |
| Direct Anti-Globulin (DAT)                    | X                      | X                | X                           | X          | X  | X                      |   |              | X                                 | X   | X                                |                             |
| RBC Phenotyping, Type and Screen              |                        | X                |                             |            |  |                        |   |              |                                   |   |                                  |                             |
| Lymphocyte Phenotype (T, B, NK cell subsets)  |                        | X                | X                           | X          | X  | X                      |   |              | X                                 | X   | X                                |                             |
| Peripheral Blood Flow Cytometry   | X                      |                  | X
(C-2 D8,
15)        |            |  |                        | X                                       |              | X                                 |   |                                  |                             |

| Procedure   | Screening              | Baseline                                    | Window Portion † |            | Triplet Combination Therapy △ | Response-Based Therapy | Disease Evaluations                         |              | End of Treatment or PD            | Active Monitoring/ Surveillance Follow-Up |                                  |                             |
|---|------------------------|---|-----------------------------|------------|--|------------------------|---|--------------|-----------------------------------|---|----------------------------------|-----------------------------|
|   |                        |   | C -2
D1                  | C -1
D1 | C1-C6
D1                              | C7-C12
D1           | Window C-1/
Pre-C1,
Cycles 6 & 12     | Cycles 3 & 9 |                                   | Safety (Day 30)                           | Follow-Up (Prior to PD)          | Survival (Post-PD)          |
| Scheduling Window (Days):   | -28 to -1  | -28 
-14* or -7 ^ | -3                          | -3         | -3                                       | -3                     | Last 7 days of the cycle                    |              | Treatment discon./PD  | +7  | Every 3 or 6 months  | Every 3 months  |
| Bone Marrow Aspiration (with flow cytometry)/ Biopsy                     | X                      |   |                             |            |  | X                      |   |              | X                                 |   |                                  |                             |
| CT Scans or MRI    | X                      | X   |                             |            |  |                        | X   | X            | X                                 |   | X                                |                             |
|  F-FDG-PET/CT Scan    |                        | X   |                             | X          |  |                        | X   |              | X                                 |   |                                  |                             |
| Symptoms/Adverse Events, Concomitant Medication Reviews                               | X                      | X   | X                           | X          | X  | X                      |   |              | X                                 | X   |                                  |                             |
| Research Tissues (archival/fresh biopsy, bone marrow biopsy/aspiration)  |                        |   |                             |            |  |                        | See Research Sample Calendar in Section 5.1 |              |                                   |   |                                  |                             |
| Research Saliva/Buccal (baseline), Blood Samples                         |                        |   |                             |            |  |                        | See Research Sample Calendar in Section 5.1 |              |                                   |   |                                  |                             |
| Survival Status   |                        |   |                             |            |  |                        |   |              |                                   |   |                                  | X                           |

**†Window Portion:** Applies only to patients enrolled in the dose expansion cohorts.

**△**Additional monitoring for TLS during C1 of triplet combination therapy is described in Section 4.1.2.

**NOTE:** Perform any other assessments and/or tests as clinically indicated at the discretion of the investigator.

 Screening and Baseline evaluations should be performed within 28 days prior to enrollment and dosing, respectively, with the following exceptions: Confirmation of diagnosis (no time limit); HIV antibody, Hepatitis B surface antigen and Hepatitis C antibody (within 3 months); Bone marrow assessments (within 12 months). See Section 2.2. **NOTE:** Any screening tests performed within the time frame for baseline do not need to be repeated.

 Within 28 days prior to dosing in Window on Cycle -1 Day 1, unless otherwise noted to be within 14 days (\*) or 7 days (^).

 To be done at treatment discontinuation (+/- 2 weeks) or may coincide with the safety follow-up visit. If treatment is discontinued for a reason other than disease progression, assessments should be repeated at the time of progression. If subject to initiate new anti-cancer therapy assessments should occur before the first dose of the new therapy.

 Follow-up prior to disease progression to occur about every 3 months (+/- 2 weeks) for first 2 years after therapy, every 6 months for years 3-5 (+/- 4 weeks), and then annually (+/- 6 weeks) at the discretion of investigator.

 After disease progression or initiation of new anti-cancer therapy, contact for survival about every 3-6 months (+/- 4 weeks).

 Physical exams to include history, vitals, weight, and height (screening only).

 Complete Blood Count with Differential will be performed prior to each dose and 3-6 hours after the first and second doses of magrolimab - Cycle 1, Days 2 and 8 for dose-finding arms (Arms 1 and 2), and Cycle -2, Days 2 and 8 for dose-escalation arms (Arms 3 and 4).

 Chemistry panels include: Acute care, Hepatic, and Mineral and 24-hour urine creatinine clearance (if needed to measure CrCl).

 Peripheral blood flow cytometry for diagnostic and staging purposes; repeat in follow-up to assess disease status and response. See also Section [5](#) for flow cytometry to be collected also for research purposes.

 Bone marrow aspiration ( $\pm$  flow cytometry)/biopsy within 12 months prior to starting treatment, unless repeat at screening/baseline felt to be clinically indicated (see Section [2.2](#)); repeat in follow-up to confirm response or progression only if bone marrow involvement is present at baseline.

 CT scans (preferred) of chest, abdomen and pelvis to be performed at each disease evaluation; may be adjusted to assess additional known sites of disease, as needed. Scans are to be done after completion of window with magrolimab and obinutuzumab (i.e., after 2 cycles of treatment; up to 7 days prior to Cycle 1, Day 1 pre-dose); after Cycle 3, Cycle 6, and Cycle 9 (if applicable), up to 7 days prior to next cycle; after Cycle 12 (if applicable), 21-28 days after completion of the treatment

 PET scans to be performed at baseline, after completion of the window with magrolimab and obinutuzumab, after Cycles 6 and 12 (if applicable), and at the end of treatment; repeat additionally if clinically indicated

 If adequate archival tissue at baseline, fresh tumor biopsy is optional. Optional “on-treatment” and bone marrow sampling will be performed, as indicated in Section [5](#).

 Samples for correlative research blood and saliva (preferred)/buccal swab samples to be collected as indicated in Section [5](#).
